5.2 SAFETY VARIABLES

Prior to treatment, the subject's medical history will be reviewed, a urine pregnancy test will be performed (if applicable), and a physical examination will be conducted. During Ultherapy® treatment, the subject's pain levels will be monitored using a validated Numeric Rating Scale (**Attachment B**). Pain scores should be obtained following each completed pass for each axilla treated. The average pain score for the entire axilla treated will then be recorded. At each subsequent visit, the subject will be queried about adverse events and changes in concomitant medications, and the treatment area will be visually examined. Additional pregnancy screening tests will be performed (if applicable) prior to treatment #2 and at the 90-day follow-up visit.

5.3 OUTCOME MEASURES

The Hyperhidrosis Disease Severity Scale (HDSS)

The Hyperhidrosis Disease Severity Scale (HDSS) (**Attachment A**) is a validated scale used for primary axillary/underarm hyperhidrosis patients. It provides a qualitative measure of the severity of their condition based on how it affects their daily activities. Patients select the statement that best reflects their experience with underarm sweating. It is a 4-point scale, with the following descriptors:

1. My underarm sweating is never noticeable and never interferes with my daily activities
2. My underarm sweating is tolerable but sometimes interferes with my daily activities
3. My underarm sweating is barely tolerable and frequently interferes with my daily activities
4. My underarm sweating is intolerable and always interferes with my daily activities

Gravimetric Sweat Production

Reduction of at least 50% from baseline in the average spontaneous axillary sweat production per subject (left and right axilla), i.e., up to 40 data points per time point, assessed by gravimetric method.

Gravimetric method is performed by drying the surface of the skin, then applying a pre-weighed filter paper to the axilla for a period of time (5 min) measured by a stopwatch. The paper is then weighed and the rate of sweat production is calculated in mg/5 min based on the difference in end weight and pre-weight.

Start Iodine Test

Performed to assess area of efficacy. Starch Iodine test is performed by applying an iodine solution to the sweaty area. After it dries, starch is sprinkled on the area. The starch-iodine combination turns a dark blue color wherever excess sweat is present. Digital images of the starch iodine test will be obtained.

5.3.1 PRIMARY ENDPOINT

The primary endpoint of this study is HDSS score reduction from a 3 or 4 at baseline to a 1 or 2 at 30 days post-treatment #2.

5.3.2 SECONDARY ENDPOINTS

The secondary endpoints of this clinical trial include:

1. A reduction in spontaneous axillary sweat production assessed by gravimetric method at all time points following completion of study treatment(s), as measured by a 50% reduction or more compared to baseline.

- a. Gravimetric method is performed by drying the surface of the skin, then applying a pre-weighed filter paper to the axilla for a period of time measured by a stopwatch. The paper is then weighed and the rate of sweat production is calculated in mg/min.
2. HDSS score reduction from a 3 or 4 to a 1 or 2 at 90 days post treatment #2.
3. Starch iodine test to assess area of efficacy.
 - a. Starch Iodine test is performed by applying an iodine solution to the sweaty area. After it dries, starch is sprinkled on the area. The starch-iodine combination turns a dark blue color wherever excess sweat is present. Digital images of the starch iodine test will be obtained.

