I understand that this investigation will be monitored by the Study Sponsor and/or a designee employed by the Study Sponsor. This monitoring will involve periodic inspection of my investigational site and ongoing review of the data that is submitted by me to the Study Sponsor. All study data will be entered within 1 week after the targeted study follow-up visit. I am also aware that I may be inspected by a representative of the relevant regulatory authorities, including the United States Food and Drug Administration, to verify compliance with applicable regulations related to clinical research on human subjects.

My current curriculum vitae and the curriculum vitae of physicians/licensed practitioners at this institution who will participate as co-investigators/sub-investigators in this study will be provided to the Study Sponsor. These curriculum vitae will include the extent and type of our relevant experience with pertinent dates and locations.

I certify that I have not been involved in an investigation that was terminated for non-compliance at the insistence of the Study Sponsor, the IRB or EC, or other regulatory authorities. I agree to provide the Study Sponsor sufficient, accurate financial disclosure information. I also agree to update financial disclosure information if any relevant changes occur during the investigation and for one year following the completion of the study.

I understand that this study protocol and the trial results are confidential, and I agree not to disclose any such information to any person other than a representative of the Study Sponsor or the relevant competent authorities without the prior written consent of the Study Sponsor.

Accepted by:

Principal Investigator Signature

Date

Principal Investigator Name

Co-/Sub-Investigator Signature

Date

Co-/Sub-Investigator Name

PROTOCOL SYNOPSIS

Company Name:	Ulthera, Inc., Merz Device Innovation Center (MDIC)
Protocol Number:	ULT-218
Protocol Title:	Evaluation of the Ulthera® System for Treating Axillary Hyperhidrosis
Investigational Device:	Ulthera® System
Development Phase:	Pilot
Study Objective:	To evaluate the Ulthera® System and the 7-3.0mm transducer for treating axillary hyperhidrosis.
Study Design:	Prospective, multi-site, non-randomized
Number of Subjects:	N = 20 treated subjects; subjects enrolled may be greater than subjects treated

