At 30 days after second treatment (day 60 of trial), the response rate, as measured by HDSS, in the active treatment group was 67%, a significant difference compared to 0% in the sham group ($p = 0.005$, two-sided Fisher's exact test (FET)). Response to active treatment peaked 7 days after the second treatment (83%) and was sustained for the remainder of the trial. Ninety days after the second treatment (day 120 of the trial), 67% of subjects were still in response. Gravimetric measurement of sweat production showed similar results. At all follow-up study visits, sweat production decreased from baseline by at least 50% in the active treatment group but not in the sham group. Regardless of study visit, percent change from baseline in gravimetric measurement was significantly greater in the active treatment group than in the sham group ($p < 0.0001$, rank-based repeated measures analysis of variance). In the active treatment group, the greatest change from baseline (73.1%) was at 90 days after the second treatment (day 120 of the trial). Starch iodine testing qualitatively supported a reduction in sweat production in the active-treated subjects compared to sham-treated subjects. All but one subject at 30 and 90 days after second treatment and two subjects at 60 days after second treatment in the active-treated group were satisfied or very satisfied. None of the sham-treated reported satisfaction at any time point after the second treatment. Treatment-related AEs reported in the active-treated group were bruising in 3 subjects (15%) with an average duration of 3.3 days (range 2-5 days), soreness or tenderness in subjects (83%) lasting an average of 12.9 days (range 4-31 days) during which only 2 subjects took a single dose of ibuprofen the day after treatment, numbness in 1 subject (8%) lasting 13 days, and paresthesia in 3 subjects (25%) lasting an average of 13.3 days (range 10-18 days). Treatment related AEs reported in the sham-treated group were soreness in 2 subjects (25%) lasting 1 day, and paresthesia in 1 subject (12.5%) lasting 1 day. Average pain scores for both transducers during both treatments for the sham-treated group were 0.8 (range 0-5) while pain scores averaged 1.8 (range 0-5 for the active-treated group suggesting that blinding was sufficient).

Pilot study results suggest the Ulthera® System may be efficacious and safe for the treatment of axillary hyperhidrosis.

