2.2 TYPE AND DESIGN OF STUDY

This study is a prospective, multi-center, non-randomized clinical trial. Up to 20 subjects who are naïve to Ultherapy for treatment of hyperhidrosis will be enrolled if all entrance criteria are met confirming eligibility for study treatment. Subjects will be treated using the Ulthera® System by the study investigator, sub-investigator or delegated clinician, receiving treatment in a 3 x 4 grid, 12 treatment squares, 60 lines of treatment per square, at one treatment depth (3.0mm), at 0.30 J of energy.

Ultrasound images will be captured of each axilla prior to the first study treatment to assess dermal thickness and depth of sweat glands. A gravimetric measurement of sweat production, starch iodine test, and pregnancy screening test, if applicable, will be performed prior to each study treatment. Digital images of the starch iodine test will be obtained. HDSS scores will be obtained prior to each treatment. During treatment, the average Numeric Rating Scale (NRS) score will be obtained by axilla treated.

Following the completion of study treatment(s), follow-up visits will be at 30, and 90 days post-treatment to assess safety and efficacy. Gravimetric sweat production measures and starch iodine tests will be completed at treatment visit #2 and at all follow-ups for all study groups. Digital images of the starch iodine test will be obtained. HDSS scores will be obtained at the treatment visit(s) and at all follow-ups for all study groups.

Efficacy will be determined by HDSS score reduction from a 3 or 4 at baseline to a 1 or 2 at 30 days post-treatment. Subject Gravimetric results, Starch iodine results, and HDSS scores at all follow-ups will also be analyzed as secondary outcomes.

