4.5 SUBJECT RANDOMIZATION AND TREATMENT GROUP ASSIGNMENT

Subjects are not randomized in this study. They will all be treated using the same treatment approach (see Section 5.1 for Study Treatment details).

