6. STATISTICAL ANALYSIS

For a given parameter, data will be summarized for each time point for which data for that parameter are available. Summaries will be displayed by time point. Subjects with incomplete data will be included in summaries for which they have data available. Baseline will be defined as the most recent observation before the first treatment. Categorical variables will be summarized as frequencies and percentages in each category. Continuous and ordinal variables will be summarized as numbers of subjects, means, standard deviations, medians, and ranges. For the primary efficacy outcome, two-sided 95% confidence intervals will be calculated for differences in proportions between study groups. All programs for data output and analyses will be written in SAS® version 9.2 or higher (SAS Institute, Inc., Cary, NC).

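### Weighed sweat, the only quantified efficacy measure that is not self-rated, has a 50% yes/no endpoint with no interval, no planned within-subject estimate and no link to the HDSS primary

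*Combined protocol and SAP*

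**What the plan says.** The primary endpoint (5.3.1) is "HDSS score reduction from a 3 or 4 at baseline to a 1 or 2 at 30 days post-treatment #2". Section 5.3 makes clear that this is a self-rating: "Patients select the statement that best reflects their experience with underarm sweating". The synopsis plans "N = 20 treated subjects; subjects enrolled may be greater than subjects treated", and section 4.5 states: "Subjects are not randomized in this study". All subjects get the same treatment and no sham is planned.

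Sweat is weighed over 5 minutes in each axilla. Section 2.2 says: "Gravimetric sweat production measures and starch iodine tests will be completed at treatment visit #2 and at all follow-ups". The schedule (Table 3.1-1) adds a reading at screening. The endpoint in 5.3.2 is a reduction "as measured by a 50% reduction or more compared to baseline", at all time points after study treatment; the synopsis names 90 days only. Section 5.3 applies the 50% rule to the average of the two axillae per subject, yet counts up to 40 data points per time point.

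On analysis, section 6 says: "Continuous and ordinal variables will be summarized as numbers of subjects, means, standard deviations, medians, and ranges". Its one planned confidence interval is for the primary outcome, as a difference in proportions between groups. Section 2.2 lists gravimetric, starch iodine and HDSS results at all follow-ups as secondary outcomes. No section names change from baseline in sweat as a quantity to estimate, and none tabulates sweat against HDSS in the same subject.

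**The concern.** With a self-rated primary endpoint, one group and no sham, an expectation effect cannot be separated from a treatment effect on HDSS alone. Weighed sweat at the same visits is the natural check. Starch iodine images are also not self-rated, but no scoring or area measurement is specified for them, so gravimetry is the only such measure that yields a number.

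The plan leaves that check weaker than the data allow in three ways:

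- The named endpoint reduces a weight in milligrams to a yes/no and gives it no interval.
- The per-visit means and SDs do not describe the change within subjects.
- Two separate response rates do not show whether the subjects who feel better are those who sweat less.

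At stake is how well a 20-subject pilot can say how much sweat fell, how precisely, and whether the HDSS result is matched by measured sweat in the same people.

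**Working it through.** **1. Figure in the documents.** This trial states no power, SD or sample-size calculation. The one reproducible result nearby is the earlier pilot's HDSS comparison (1.6.5): 67% of 12 active subjects is 8/12, against 0/8 on sham. The two-sided Fisher's exact test gives p = 0.0047, which agrees with the stated 0.005.

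**2. Information kept by a yes/no cut.** Assume the log of follow-up over baseline sweat is roughly normal. For estimating a shift, the efficiency of the dichotomised result relative to the continuous one is φ(z)² / [p(1 − p)], where p is the share past the cut and z its normal quantile. The documents give no gravimetric responder rate, so p is varied.

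| Assumed p | φ(z) | Efficiency | Loss | 20 subjects worth |
|---|---|---|---|---|
| 50% | 0.399 | 0.637 | 36% | 12.7 |
| 66.7% | 0.364 | 0.595 | 41% | 11.9 |
| 75% | 0.318 | 0.539 | 46% | 10.8 |
| 90% | 0.175 | 0.342 | 66% | 6.8 |

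If the target is the responder proportion itself, estimated through a normal model with the SD unknown, the loss is about 34% to 38% over p from 50% to 90%.

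**3. What the intervals would look like.** For 14/20 responders the exact (Clopper-Pearson) 95% CI is 45.7% to 88.1%. For a geometric mean reduction of 70%, the 95% limits of the ratio are 0.3 × exp(±2.093 × SD/√20):

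- Assumed log SD 0.8: half-width 0.374, so a reduction of 56% to 79%.
- Assumed log SD 1.0: half-width 0.468, so a reduction of 52% to 81%.

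These are different quantities (share of subjects, average reduction), so the widths are not directly comparable. The plan provides an interval for neither.

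**4. Why per-visit means and SDs are not enough.** The SD of a paired change is √(s₁² + s₂² − 2r·s₁·s₂). With equal SDs s it is s√[2(1 − r)]: 1.41s at r = 0, 1.00s at r = 0.5 and 0.45s at r = 0.9. The correlation r between visits is not among the planned summaries, so a within-subject interval cannot be recovered from them.

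**5. Why two rates do not give the link.** Suppose 70% respond on each measure. The share meeting both can lie anywhere from 0.70 + 0.70 − 1 = 40% up to 70%, that is 8 to 14 of 20, with exact 95% CIs of 19% to 64% and 46% to 88%. Only a cross-table settles which.

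**6. Baseline and entry rule.** Entry requires at least 50 mg per axilla (4.3.1). The schedule places the pre-treatment gravimetric test at screening, and section 6 takes the last reading before treatment as baseline. The qualifying reading can therefore be the baseline, which allows regression to the mean. As an illustration with no true change and no selection, a subject crosses the 50% cut by noise with probability Φ(ln 0.5 / (s√2)). This is 5% at an assumed per-occasion log SD of 0.3 and 21% at 0.6.

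**The case against.** The plan does more than the yes/no endpoint. Section 6 summarises every parameter at every time point, including visit #2, and section 2.2 has gravimetry analysed at the same follow-ups as HDSS. This stands: the loss in step 2 belongs to the named endpoint and not to everything the trial will report.

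Several stronger readings are tempting, and the documents do not support them:

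- *Gravimetry is the only objective measure, so the primary goes uncorroborated.* Starch iodine images are a second measure that is not self-rated, and sweat is reported at the HDSS visits. What is missing is a pre-specified link within subjects.
- *The plan retreats from the pilot's method.* The pilot did report that "percent change from baseline in gravimetric measurement was significantly greater in the active treatment group", using repeated measures. That was a comparison of active with sham, which has no counterpart in a one-group study, and the pilot also used 50% as a reference point.
- *Power is thrown away.* No hypothesis test is planned. For a true 40% reduction, simulated power to show a fall is 77% (continuous) against 44% (responder rate) at an assumed log SD of 0.8. At 70%, close to the pilot's best visit (73.1%), it is about 100% against 99.9%, and at SD 1.0 it is 99.9% against 98.1%. Part of the gap at 40% also comes from the discreteness of the exact method.
- *About 40% is a fixed loss.* It arises only by borrowing the pilot's 67% HDSS rate as a gravimetric rate.

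It is also fair to say that a continuous estimate is no protection against bias. Regression to the mean would enter the geometric mean reduction as well. With 20 subjects the link will be imprecise too: an observed correlation of 0.5 has a 95% CI of 0.07 to 0.77.

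**Conclusion.** The point holds as a cheap improvement to a descriptive plan. On the text, the gravimetric endpoint is a 50% responder cut without an interval, no within-subject change is named for estimation, and nothing ties sweat reduction to HDSS response in the same subject. With a self-rated primary and no control, that link is worth pre-specifying.

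The size is a loss of about 36% to 46% of the information in the named endpoint, assuming roughly normal log-ratios and responder rates of 50% to 75%. It would be larger at higher rates. No gravimetric SD or responder rate in the documents narrows this. If the effect is as large as in the pilot, either analysis would show that sweat fell. The gain then lies mainly in a stated size of reduction with its precision, and in the cross-table. Nothing here shows that the trial's conclusion would be wrong under the present plan.

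**What to change.** In 5.3.2 and 6.1:

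1. Keep the 50% responder rate, computed on the per-subject average of both axillae (20 values), with an exact 95% CI.
2. Add the within-subject change from baseline at visit #2, 30 days and 90 days: the geometric mean percent reduction from log-ratios with a 95% CI, or a Hodges-Lehmann estimate and interval for percent change if readings of zero occur.
3. Add a cross-table of HDSS response by 50% gravimetric response at 30 and 90 days, with the proportion meeting both and its exact 95% CI.
4. State that without a control these estimates include any regression to the mean arising from the 50 mg entry rule.
5. Reconcile the timing (90 days only in the synopsis, all time points in 5.3.2) and say whether visit #2 counts. Reconcile the unit in 5.3 (per-subject average against 40 data points).

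The cost is some analysis wording and two tables, with no new visits or measurements. The both-criteria rate cannot exceed the HDSS rate, so one reported figure may look less favourable.

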5.4 FOLLOW-UP

Subjects will be asked to return to the clinic for follow-up visits at 30 and 90 days post-treatment #2.

The following assessments will be completed at all follow-up visits: gravimetric assessment, starch iodine test, and HDSS. Digital images of the starch iodine test will be obtained. At the last follow-up visit, a pregnancy screening test will be completed, if applicable. Safety endpoints and adverse events will be monitored at all follow-up visits.

5.5 PROTOCOL DEVIATIONS

This study should be conducted as described in this protocol, except for an emergency situation in which the protection, safety, and well-being of a subject requires a protocol deviation, based on the judgment of the investigator (or a responsible, appropriately trained professional designated by the investigator). If the deviation from the protocol is necessary to protect the physical well-being of a subject in an emergency, such protocol deviations must be reported to the Sponsor and the reviewing IRB or EC as soon as possible, but no later than five working days after the emergency occurred.

In the event of a significant deviation from the protocol due to an accident or mistake, the investigator or designee must contact the Sponsor at the earliest possible time by telephone to discuss the deviation and its impact on the study and subject continuation in the study. These discussions will be documented by the investigator and the Sponsor, and reviewed by the monitor.

5.6 WITHDRAWAL CRITERIA AND PROCEDURES

All subjects have the right to withdraw at any point during the study without prejudice. The investigator can discontinue any subject, at any time, if medically necessary. The reason for subject's withdrawal should be documented on the appropriate study-specific data form. The subject must undergo the recommended follow-up assessments specified for the last study visit unless contraindicated due to a medical condition. Withdrawn subjects will not be replaced.

5.7 END OF STUDY (COMPLETION)

All subjects who have signed an Informed Consent Form, except for screen failures, will be considered enrolled in the study. Subjects who complete the study duration will be considered to have completed the study. Any subject who does not return for a scheduled follow-up visit will be contacted at least twice by telephone to determine the cause for the missed visit and to try to get the subject scheduled for the follow-up. A new visit will be scheduled as soon as possible. All subjects should be followed until completing the study follow-up or until study discontinuation (withdrawal) for other reasons. The reason for study discontinuation should be documented for each subject. Subjects will be deemed "Lost-to-Follow-up" if they have not returned within six weeks after the last

follow-up target. For any subject lost to follow-up at least three attempts to contact the subject must be documented; the attempts must be two phone calls/emails and a registered letter.

6. STATISTICAL ANALYSIS

For a given parameter, data will be summarized for each time point for which data for that parameter are available. Summaries will be displayed by time point. Subjects with incomplete data will be included in summaries for which they have data available. Baseline will be defined as the most recent observation before the first treatment. Categorical variables will be summarized as frequencies and percentages in each category. Continuous and ordinal variables will be summarized as numbers of subjects, means, standard deviations, medians, and ranges. For the primary efficacy outcome, two-sided 95% confidence intervals will be calculated for differences in proportions between study groups. All programs for data output and analyses will be written in SAS® version 9.2 or higher (SAS Institute, Inc., Cary, NC).

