
Treatment Outline:
	
 1. Screening/Baseline/Treatment Visit #1: 
 a. Obtain Informed Consent and medical history; b. Screen for general inclusion/exclusion criteria; c. Obtain axillary ultrasound images of each axilla; d. Perform pregnancy screening test, if applicable;

	
 e. Complete baseline evaluations: HDSS, gravimetric, and starch iodine test with digital images of the result; f. Administer local anesthetic to both axillas; g. Perform bilateral Ultherapy treatment; h. Assess Numeric Rating Scale for Pain; and i. Assess for adverse events. 
 2. Post-treatment #1 telephone contact: 
 a. Capture adverse events (7±2 days). 3. Treatment Visit #2, 30 ± 7 days post-treatment #1: 
 a. Complete HDSS, gravimetric, and starch iodine test with digital images of the result; b. Perform pregnancy screening test, if applicable; c. Administer local anesthetic to both axillas; d. Perform bilateral Ultherapy treatment; e. Assess Numeric Rating Scale for Pain; and f. Assess for adverse events. 4. Post-treatment #2 telephone contact: 
 a. Capture adverse events (7±2 days). 5. Follow-up Visits post-treatment #2 for efficacy evaluation: 
 a. 30 ± 7 days 
 i. Complete HDSS, gravimetric test, and starch iodine test with digital images of the result; and ii. Assess for adverse events. b. 90 ± 7 days 
 i. Complete HDSS, gravimetric test, and starch iodine test with digital images of the result; ii. Assess for adverse events; and iii. Perform pregnancy screening test, if applicable.

Primary Endpoint:
	
HDSS score reduction from a 3 or 4 at baseline to a 1 or 2 at 30 days post-treatment #2.

Secondary Endpoints:
	
 1. Reduction in spontaneous axillary sweat production assessed by a gravimetric method at 90 days post treatment #2, as measured by a 50% reduction or more compared to baseline. 2. HDSS score reduction from a 3 or 4 to a 1 or 2 at 90 days post treatment #2. 3. Starch iodine test to assess area of efficacy with digital images.

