3. STUDY PROCEDURES

3.1 SCHEDULE OF ASSESSMENTS AT EACH STUDY VISIT

Table 3.1-1 provides an overview of the subject screening procedure, baseline evaluation, treatment plan, and follow-up requirements.

TABLE 3.1-1 SCHEDULE OF ASSESSMENTS

Evaluation	Screening ⁺	Baseline / Treatment #1 ⁺ Day 0	Telephone Contact Day 7±2D Post-Treatment #1	Treatment #2 Day 30±7	Telephone Contact Day 7±2D Post-Treatment #2	Follow-up Intervals Post Treatment #2	
						Day 30±7	Day 90±7
Screening and Subject Consent	√						
Initial Evaluation (Includes entrance criteria, eligibility assessment, demographics, medical history, clinician assessment)	√						
Pregnancy Screen	√ [^]	√ [^]		√ [^]			√
Study Treatment		√		√			
NRS for Subject Pain Assessment		√		√			
HDSS		√		√		√	√
Gravimetric Test	√			√		√	√
Starch Iodine Test and digital images of results		√		√		√	√
Obtain Axillary Ultrasound Images	√						
AE Forms	√	√	√	√	√	√	√

+Screening and Baseline/Treatment Visits may be separate visits or combined into one visit.

[^] Pregnancy:

- a. If a subject becomes pregnant after the Baseline visit and all study treatments have been completed, the subject should continue to be followed.
- b. If a subject becomes pregnant after the Baseline visit but before any study treatments, the subject should be exited from the study.
- c. If a subject becomes pregnant after the Baseline visit but before all study treatments have been completed, additional study treatments should be discontinued and the subject should continue to be followed.

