4.3 ELIGIBILITY

4.3.1 INCLUSION CRITERIA

Subjects must meet all of the following criteria for study enrollment:

1. Male or female, age 18-75 years.
2. Subject in good health.
3. Diagnosis of bilateral axillary hyperhidrosis refractory to previous topical therapies.
4. At least 50 mg of spontaneous resting axillary sweat production in each axilla measured gravimetrically at room temperature/humidity (20 - 25.6°C/20-80%) over a period of 5 minutes. (Patients should be at rest for at least 30 minutes after physical exercise including walking.)
5. HDSS score of 3 or 4. An attempt will be made to approximate an equal number of scores 3 and 4.
6. Understands and accepts the obligation not to undergo any other procedures in the areas to be treated through the follow-up period.
7. Willingness and ability to comply with protocol requirements, including returning for follow-up visits and abstaining from exclusionary procedures for the duration of the study.
8. Subjects of childbearing potential must have a negative urine pregnancy test result and must not be lactating at the Screening Visit and be willing and able to use an acceptable method of birth control (e.g. barrier methods used with a spermicidal agent, hormonal methods, IUD, surgical sterilization, abstinence) during the study. Women will not be considered of childbearing potential if one of the following conditions is documented on the medical history:
 - a. Postmenopausal for at least 12 months prior to study;
 - b. Without a uterus and/or both ovaries; or
 - c. Bilateral tubal ligation at least six months prior to study enrollment.
9. Absence of physical or psychological conditions unacceptable to the investigator.

10. Willingness to refrain from use of aspirin, Ibuprofen, Naproxen or any other NSAID, and Vitamin E in the 2 weeks prior to each study treatment.
11. Willingness and ability to provide written informed consent prior to performance of any study-related procedure.

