22. Psychiatric drugs that in the investigators opinion would impair the subject from understanding the protocol requirements.

After subjects have provided informed consent and met the inclusion/exclusion criteria, the study procedures described in the following section will be performed. Subjects can be enrolled in the study and treated according to this protocol on the same day.

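### Under the schedule, the sweat reading that qualifies a subject is also the gravimetric baseline, so regression to the mean pushes the secondary 50%-reduction responder rate upward by an amount the documents cannot fix

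*Combined protocol and SAP*

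**What the plan says.** The baseline rule in Section 6 is general: "Baseline will be defined as the most recent observation before the first treatment". Entry under Section 4.3.1 requires "At least 50 mg of spontaneous resting axillary sweat production in each axilla measured gravimetrically" over 5 minutes.

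In the Study Overview table and again in Table 3.1-1, the row "Gravimetric Test" is ticked at Screening, Treatment #2, Day 30 and Day 90. It is blank at Baseline/Treatment #1, where HDSS and starch iodine are ticked. The footnote adds: "Screening and Baseline/Treatment Visits may be separate visits or combined into one visit". The end of Section 4.3.2 also allows same-day treatment: "Subjects can be enrolled in the study and treated according to this protocol on the same day".

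Two other places describe the pre-treatment test. Section 2.2: "A gravimetric measurement of sweat production, starch iodine test, and pregnancy screening test, if applicable, will be performed prior to each study treatment". Synopsis, Treatment Outline step 1e, under one joint Screening/Baseline/Treatment #1 heading: "Complete baseline evaluations: HDSS, gravimetric, and starch iodine test with digital images of the result".

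The gravimetric endpoint is secondary: a fall of at least 50% from baseline in each subject's left-right average (Section 5.3), at 90 days in the Synopsis and at all post-treatment time points in Section 5.3.2. The primary endpoint is HDSS. All subjects receive the same treatment (Section 4.5).

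**The concern.** A reading kept only because it reached a lower limit is, on average, above that subject's usual level whenever readings vary from day to day. A later reading then tends to be lower without any treatment effect. If the qualifying reading is also the denominator of the percent change, some of this drift is counted as response. A concurrent control would show the same drift and allow it to be subtracted; this single-arm study has none. The plan calls for no confirmatory reading, no averaging of readings and no adjustment.

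The schedule conflict adds a second problem. With separate visits, a site that follows Section 2.2 takes a fresh reading at Treatment #1, and the baseline rule selects it. A site that follows the tables does not. Baseline could then be a selected value in some subjects and an unselected one in others.

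**Working it through.** **Which reading becomes baseline**

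- Separate visits, tables followed: the Screening (qualifying) reading.
- Separate visits, Section 2.2 followed: the Treatment #1 reading, which was not used for selection; the bias largely vanishes.
- Combined visit: the single test meets the tables, Section 2.2 and step 1e together, and it is the qualifying reading.

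**Inputs**

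From the documents: 50 mg per 5 minutes in each axilla; response if the follow-up left-right average is at most half the baseline average; 20 subjects; one arm. The plan gives no gravimetric SD, expected rate or sample-size derivation, so there is no figure of its own to reproduce.

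Assumed: log-normal sweat rate; candidate median m of 50 to 200 mg; between-subject log SD σb of 0.5 or 0.8; within-subject visit-to-visit log SD σw of 0.2 to 0.7; correlation 0.7 between left and right errors at one visit; errors independent between visits.

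**Hand check of the direction, one axilla, no treatment effect**

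Let s = √(σb² + σw²) and z = (ln 50 − ln m)/s. The expected log change from the qualifying reading to a later one is −(σw²/s) × φ(z)/[1 − Φ(z)].

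With m = 100 and σb = σw = 0.5: s = 0.707, z = −0.693/0.707 = −0.980, φ/(1 − Φ) = 0.2468/0.8365 = 0.295. The change is −(0.25/0.707) × 0.295 = −0.104, and exp(−0.104) = 0.90. That is an apparent fall of about 10% with no effect. The expression is negative whenever σw is above zero.

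**Responder rates by simulation, no treatment effect**

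Subjects are kept if both axillae reach 50 mg. The same subjects are then scored against the qualifying reading and against an independent pre-treatment reading.

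| m (mg) | σb | σw | Qualifying baseline | Independent baseline | Excess (points) | Of 20 subjects |
|---|---|---|---|---|---|---|
| 50 | 0.5 | 0.2 | 0.6% | 0.4% | 0.2 | 0.04 |
| 50 | 0.5 | 0.5 | 24.9% | 14.4% | 10.5 | 2.1 |
| 50 | 0.5 | 0.7 | 39.3% | 22.4% | 16.9 | 3.4 |
| 60 | 0.5 | 0.5 | 22.4% | 14.4% | 8.0 | 1.6 |
| 100 | 0.5 | 0.5 | 17.5% | 14.4% | 3.1 | 0.6 |
| 200 | 0.8 | 0.5 | 15.5% | 14.4% | 1.1 | 0.2 |
| 200 | 0.8 | 0.2 | 0.4% | 0.4% | 0.0 | 0.0 |

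The bias is the excess column. The independent-baseline column is chance response, which a fresh reading does not remove.

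With a true 50% reduction, the rates are 50 to 72% against 50%, an excess of 0 to about 22 points (22% × 20 = 4.4 subjects at most).

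**A second reading in a combined visit**

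A repeat minutes later shares that day's conditions. With m = 60 and σb = σw = 0.5:

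- If 80% of the within-subject variance is day-to-day: qualifying 22.5%, same-day repeat 21.0%, independent 14.5%. Share of the bias removed: (22.5 − 21.0)/(22.5 − 14.5) = 1.5/8.0 = 19%.
- If 50% is day-to-day: 22.4%, 18.5% and 14.5%. Share removed: 3.9/7.9 = 49%.

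**The case against.** The strongest reply is that this is a pilot of 20 subjects and the endpoint is secondary, with no success threshold, test or power claim attached. Every variance and median above is assumed, and the excess is negligible if readings are stable or candidates sit well above 50 mg: at a median of 200 mg and σw of 0.5 it is about 0.5 to 1 point. All of that stands, and it limits the weight of the point.

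The reply can also cite the earlier sham-controlled pilot (Sections 1.6.5 and following text), which used a similar entry rule. Its sham group did not show a 50% fall in sweat production at any follow-up visit. This is the only empirical evidence in the documents, and it is weak evidence against a very large effect. It comes from 8 subjects, and no sham responder rate on the gravimetric rule is given. It also does not exclude the sizes shown here: with candidate medians of 60 to 100 mg, the median apparent fall without treatment is at most about 33%.

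Three stronger readings are tempting, and the documents do not support them.

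- A reader might infer that the protocol already requires a second test in every subject. It does so at most when the visits are separate; in a combined visit nothing calls for one.
- A reader might take the whole false-responder rate, up to 39.3%, as the bias. Most of it is chance variation that remains with a fresh baseline and reflects the missing control arm.
- A reader might conclude that HDSS is protected because it is ticked at Baseline. It is not: a score of 3 or 4 is an entry criterion, and that score is also the only scheduled pre-treatment value, so the primary endpoint has the same exposure.

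**Conclusion.** The point holds for the secondary gravimetric responder rate. The direction follows from the documents alone: one scheduled pre-treatment test, a lower limit for entry on that test, a baseline rule that selects it, and no control. The size does not. Under the stated assumptions the excess is about 0 to 17 points with no treatment effect, and about 1 to 8 points (0.2 to 1.6 of 20 subjects) at a within-subject log SD of 0.5 with candidate medians of 60 to 200 mg. The conflict between the schedule tables and Section 2.2 is real for separate visits only. The point does not show that an observed gravimetric response would be mostly artefact, and correcting the baseline would not replace a control arm.

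**What to change.** 1. Tick the gravimetric test in the Baseline/Treatment #1 column of the Study Overview table and Table 3.1-1, so that both agree with Section 2.2.
2. In Section 6, define gravimetric baseline for separate visits as the Treatment #1 pre-treatment reading, not the eligibility reading. Keep eligibility on the Screening reading, so that the new baseline is not itself selected.
3. For combined visits, a second 5-minute reading taken after eligibility is confirmed may serve as baseline. Because it removes only part of the bias, flag these subjects and report the responder rate by visit structure.
4. State regression to the mean as a limitation of both the gravimetric and the HDSS responder rates.

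The cost is one 5-minute filter-paper test per subject and a responder rate that may be less favourable. Sample size and the entry threshold are unchanged. Section 6 already provides medians for continuous variables, so no new summary is needed to show the typical change.
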